were found (76 ppb – 104 ppb); this range is based on four samples collected during May-July 1982 with a mean of 85.5 ppb. PCE is a dry cleaning solvent. In the one sample taken in 1985 before the contaminated wells were shut down, a PCE level of 215 parts per billion was found. In addition, TCE, a degreaser, and 1,2-dichloroethylene (DCE), a breakdown product of PCE were also detected in this sample. The contaminated wells were closed in February 1985 (ATSDR 1997).

! **Hadnot Point.** This water distribution system supplied water primarily for industrial purposes at the base but it also supplied drinking water to the Hospital Point housing area. High levels of TCE (a maximum of 1,400 ppb) were detected during sampling in 1982. High levels of TCE and DCE were found during the routine testing of the drinking water system in 1984 and 1985. The Hadnot Point system has 39 operational wells, although only approximately 20 wells were used at any one time. The contamination was linked to leaking on-base underground storage tanks.

[**Holcomb Boulevard.** In 1972, the Holcomb Boulevard system went on-line and served the Midway Park, Berkeley Manor, Watkins Village, and Paradise Point areas of base housing. Before 1972, the Holcomb area was served by the Hadnot Point water distribution system. In early 1985, a fuel line accidentally burst at the Holcomb Boulevard water distribution system, releasing fuel into the water supply. To remediate the problem, the Holcomb water supply was provided by an emergency line from the Hadnot Point system. The emergency hookup occurred over a 12-day period starting on January 27, 1985. During this period, the Holcomb area base housing received contaminated water from the Hadnot Point system. Once the fuel line was repaired, the emergency hookup from Hadnot Point was disconnected, and the Holcomb Boulevard system resumed service to its designated housing areas.

Each of the affected housing areas received water containing a mixture of several contaminants, a phenomenon noted with almost every population exposed to contaminants released from hazardous

waste sites.

ATSDR's 1997 public health assessment (PHA) for Camp Lejeune found that PCE was the primary contaminant at ABC One-Hour Cleaners (ATSDR 1997). PCE and other solvents from the dry cleaning establishment had contaminated a nearby well on Camp Lejeune property that provided drinking water to the Tarawa Terrace family base housing.

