In response to the PHA recommendation, ATSDR began the multi-step process of determining the appropriateness of conducting an epidemiological study of specific childhood cancers and birth defects at Camp Lejeune. The first step was to determine which childhood health problems to study. Based on the scientific literature, ATSDR decided to focus on specific childhood cancers and birth defects: childhood leukemia, spina bifida, anencephaly, cleft lip and cleft palate.

The second step was to identify the children eligible for the study by doing a telephone survey. ATSDR decided on children born to women who were pregnant with them while living on the base during 1968–1985. The year 1968 is the starting point because that year North Carolina began computerizing its birth records. These records were used to identify children for the study. The end point is 1985 because the tainted wells were shut down that year.

The survey began in September 1999 and ended in January 2002. ATSDR surveyed by telephone the parents of 12,598 eligible children. This number was about 80% of the estimated total. Parents were asked if the child had had a birth defect or had developed a childhood cancer. A total of 99 cases of childhood leukemia, spina bifida, anencephaly, cleft lip and cleft palate were reported (Appendix II).

The third step was to confirm the children's health problem(s). ATSDR asked the parents who reported that their children had health problems of interest (or the children if they were now over 18) for access to their child's health records. These records are now under review. ATSDR has received records for 60 of the 99 children so far and has confirmed about 80% as being correctly reported.

The final step will be to conduct a case-control study. This study will include all confirmed cases of the birth defects and childhood cancers which are the focus of the study. The study will also include modeling of the water system to see which mothers did and did not receive the water with VOCs. Currently we do not know which mothers received the water with VOCs.

In summary, ATSDR has finished the survey and is now confirming the cases. These steps were needed to prepare for the larger study. There is enough information to proceed with the full study. Only the case-control study can establish whether VOC-tainted drinking water may cause the childhood health problems being studied.

Intended/Potential Use of Study Findings

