To date, information regarding the health effects of exposures to drinking water contaminated with TCE and PCE are extremely limited. The findings of this study at Camp Lejeune should further our understanding of the health effects of TCE or PCE exposure from community drinking water and will help us better focus our prevention efforts.

Study Design/Locations

ATSDR will conduct a case-control study of cases of childhood cancer or specific birth defects and a random sample of controls to assess the relationship between VOC exposure and the incidence of childhood cancer and birth defects in children born to parents while residing at Camp Lejeune from 1968 to 1985. Both cases and controls may currently reside anywhere in the United States.

Objectives

The overall objective of this study is to examine the associations between maternal exposures within a 1-year period before child's birth to TCE and PCE in drinking water at Camp Lejeune during the period of 1968-1985 and risk of specific birth defects and childhood leukemia (ALL) in offspring.

Hypotheses

1. a. There is no association between ever drinking TCE/PCE contaminated water during the first trimester and the risk of specific birth defects.

- b. There is no association between ever drinking TCE/PCE contaminated water during each trimester and the risk of leukemia (ALL).
- 2. a. There is no association between exposures to different concentrations of TCE/PCE in drinking water during the first trimester and the risk of developing specific birth defects.
 - b. There is no association between exposures to different concentrations of TCE/PCE in drinking water during each trimester and the risk of leukemia (ALL).
- 3. a. There is no association between exposures during the first trimester to ever/never or to different concentrations of TCE/PCE in drinking water, taking into account the amount of water used (i.e., showering, hand washing dishes) or consumed by the mother, and the risk of specific birth defects.
 - b. There is no association between exposures during each trimester to ever/never or to different concentrations of TCE/PCE in drinking water, taking into account the amount of water used (i.e., showering, hand washing dishes) or consumed by the mother, and the risk of leukemia (ALL).

METHODS

Study Rationale

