In order to provide a quantitative estimate of exposure, spatial and temporal distributions of contaminant-specific compounds are required for the duration of the study (1968–1985). Ideally, tap samples of household water for contaminant-specific compounds would be required for each study subject. Owing to the paucity of historical, contaminant-specific data, this approach is not possible. An alternative approach is to reconstruct estimates of the spatial and temporal distribution of the contaminant-specific compounds at locations (such as residences) serviced by a water-distribution system, including the residence locations of study subjects. Using an approximation technique, such as water-distribution system modeling, can provide the proportional contribution of water from a water source to any location serviced by the water-distribution system. This technique can also provide the relative concentrations of contaminant-specific compounds mixed with the water delivered to study subject residences. Such an approach has been successfully used in two epidemiological studies that have gained national attention.

In Woburn, Massachusetts, water-distribution system modeling was used to provide contaminated public water exposure estimates for subject residences (Murphy 1991; Costas et al. 2002). Specifically, Murphy (1991) developed a water-distribution system model to estimate the distribution of contaminated water potentially delivered to each Woburn residence from contaminated wells G and H. In Dover Township, New Jersey, results of water-distribution modeling were used to develop exposure indexes for

historically contaminated public water supply in a case-control study of childhood cancers (Maslia et al. 2001; NJDHSS 2003). In this analysis, Maslia et al. (2001) applied the concept of proportionate contribution, derived from results of water-distribution system modeling, to estimate the percentage of water delivered to any study location for any source of public water. This analysis reconstructed the monthly distribution of water from January 1962–December 1996.

In applying the estimation method described above (historical reconstruction using water-distribution system modeling) to the proposed case-control study, the following protocol will be used:

- I. Development of a computerized network model of the present-day water distribution system;
 - (a) field-data collection of the present-day system operations; and

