 - (b) hydraulic and water-quality calibration and testing of the present-day model based on the field data;
- II. Development of historic distribution system models through the study period, 1968–1985;
 - (a) historical reconstruction of hydraulics within the water-distribution system;
 - (b) historical reconstruction of fate and transport of contaminants within the water-distribution system;
 - (c) comparison of historical contaminant concentrations with measured tap sample data for specified locations and times; and
 - (d) assignment of the monthly contaminant concentrations for historical period for all study locations.

The exposure assessment methods in the current study will most likely estimate concentrations by year and housing complex. However, depending on the completed model, it may be necessary and possible to estimate contaminant levels at different locations within each housing complex.

Study Population

The 1998 ATSDR adverse pregnancy outcomes study at Camp Lejeune obtained birth certificate information on the 12,493 children born to parents known to have been stationed at Camp Lejeune during pregnancy between 1968 and 1985. These years were chosen because 1968 is the first year that birth

certificates were computerized in North Carolina and 1985 is the last year that VOC contamination was detected at the base. This time period also provided a sufficient sample size to conduct the study. An estimated additional 4,000 births occurred elsewhere to personnel who were stationed at Camp Lejeune at some point during pregnancy during the 1968-1985 timeframe (ATSDR 2003). A referral process was used to obtain information on personnel who were pregnant while residing at Camp Lejeune during 1968-1985 but who delivered elsewhere. Additionally, a media campaign was used to find personnel stationed at Camp Lejeune during pregnancy who could not be located as well as the estimated 4,000 births that occurred elsewhere. Names of personnel identified through referral or by the media campaign were cross-referenced with military databases.

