A 1999-2002 ATSDR survey located 12,598 children born to parents who resided at Camp Lejeune at any time during pregnancy between 1968 and 1985. Children eligible for the survey were those born at 28 weeks or more gestation to mothers who were pregnant while they lived in base housing at Camp Lejeune during 1968-1985. Survey respondents were asked basic demographic questions as well as if the child was diagnosed with cancer before age 20 or if the child was diagnosed with a birth defect before age 5. If the child had cancer or a birth defect, the type of cancer or birth defect was also collected. Parental reports of cancer and birth defects are being verified by reviewing medical records. If medical records are not available to confirm a case, we will use other appropriate documentation such as the birth certificate, death certificate, or information obtained from a recent doctor's visit (e.g., a dental visit for potential cleft cases or physical therapy records for potential spina bifida cases) (Appendices VI, VII, VIII). The following cases of selected birth defects and cancers have been reported: 35 neural tube defects (NTDs), 42 oral cleft defects, and 22 childhood leukemias. To date, records have been obtained for 20 NTDs (15 confirmed as having NTDs; 5 confirmed as not having NTDs), 1 was ineligible, 1 refused, and 13 are still pending. Records have been obtained for 23 oral cleft defects (20 confirmed as having oral cleft defects; 3 confirmed as not having oral cleft defects), 3 refused, and 16 are still pending. Records have been obtained for 17 childhood leukemias (12 confirmed as having leukemia; 5 confirmed as not having leukemia), 2 were ineligible, and 3 are still pending.

Eligibility (Participant inclusion/exclusion criteria)

Potential cases consist of children with the following birth defects or childhood cancers who were born to mothers who resided at Camp Lejeune during their pregnancies between 1968 and 1985: NTDs (consisting of anencephaly and spina bifida), oral clefts (consisting of cleft lip with and without cleft palate and cleft palate), and childhood leukemias. Familial cases of leukemia, children who were 20 years of age or older when diagnosed with leukemia, or children who were 5 years of age or older when diagnosed with NTDs or oral clefts will be excluded. Only confirmed cases will be included in the primary analyses. We will consider doing a secondary analysis including unconfirmed cases.

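### The water model starts in January 1968, up to a year after the exposure window opens for children born in 1968; the gap is small, about one case per outcome

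*Protocol*

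**What the plan says.** **Model period.** The Exposure Assessment section says that contaminant distributions are needed for 1968–1985. Step II is "Development of historic distribution system models through the study period, 1968–1985", and step II(d) assigns monthly concentrations to the study locations for that historical period.

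**Population start.** The Justification for Study gives an administrative reason for the first year: "The year 1968 is the starting point because that year North Carolina began computerizing its birth records". The Study Population section repeats it. The source survey "located 12,598 children born to parents who resided at Camp Lejeune at any time during pregnancy between 1968 and 1985", and the Eligibility section takes as cases children "born to mothers who resided at Camp Lejeune during their pregnancies between 1968 and 1985". Neither requires conception in 1968 or later.

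**Exposure window.** The Objectives concern "maternal exposures within a 1-year period before child's birth to TCE and PCE in drinking water at Camp Lejeune", and Data Analysis uses the same one-year period. The hypotheses test the first trimester for birth defects and each trimester for leukemia. The Discussion also promises pre-conception and whole-pregnancy windows.

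**Residence.** Data Collection takes the mother's residential history for one year either side of the birth, so for the earliest births it reaches back to January 1967.

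**The concern.** Both the births and the water model begin in 1968, but exposure precedes birth by up to a year. A child carried to term and born in January 1968 had its first trimester in spring and early summer 1967. The plan collects where the mother lived in those months but reconstructs no water concentrations for them. It also does not extend the model, exclude these births or say how unmodelled months are to be handled.

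The water of 1967 cannot be presumed clean. The Introduction says that the Tarawa Terrace supply well, drilled in 1958, was probably contaminated soon afterwards. If blank months were read as zero, some exposed pregnancies would enter the reference group, which Data Analysis defines as children exposed to neither chemical. If the children were dropped, a few would be lost from a study with very few cases.

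**Working it through.** The plan gives no figure for this gap, so there is none to reproduce.

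**Inputs from the protocol**
- Model start: 1 January 1968.
- Births: 1968–1985, which is 18 × 365 + 5 leap days = 6,575 days.
- Expected participating cases: 25 neural tube defects, 32 oral clefts and 14 leukemias.
- Exposure prevalence used for the power statement: 40%.

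**Assumptions not in the protocol**
- Births are spread evenly over the 6,575 days.
- Gestation is 280 days from the last menstrual period.
- The first trimester is the first 91 days.
- Every mother lived on base throughout the window. This makes the results upper bounds.

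**Check on one birth.** For a birth on 1 January 1968, the last menstrual period is 27 March 1967, the first trimester ends on 25 June 1967, and the one-year window opens on 1 January 1967. All of this precedes the model.

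**Share of births affected**

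| Part of window before 1968 | Last birth date affected | Days | Share |
|---|---|---|---|
| Whole first trimester | 8 July 1968 | 190 | 190/6,575 = 2.9% |
| At least part of first trimester | 6 October 1968 | 280 | 280/6,575 = 4.3% |
| At least part of one-year window | 30 December 1968 | 365 | 365/6,575 = 5.6% |

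With gestation from 28 weeks (the survey minimum) to 42 weeks, the first share runs from 1.6% to 3.1% and the second from 3.0% to 4.5%.

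**Cases per outcome.** Outcomes are analysed separately, so the count per outcome is what matters.

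| Outcome | Whole first trimester (2.9%) | At least part (4.3%) |
|---|---|---|
| 25 neural tube defects | 0.7 | 1.1 |
| 32 oral clefts | 0.9 | 1.4 |
| 14 leukemias | 0.4 | 0.6 |

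Of the 710 planned controls, the same shares give about 21 and 31.

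**Effect if the affected children were coded unexposed.** Let f be the affected share, the same in cases and controls. With control exposure p0 = 0.40 and case exposure p1 = OR × p0 / (1 − p0 + OR × p0), each proportion is multiplied by (1 − f). Taking f = 4.3% treats a partial loss as a total one, which is the harsher case.

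- OR 2.5, so p1 = 0.625. At f = 2.9%, the proportions become 0.6069 and 0.3884. The OR is (0.6069/0.3931) / (0.3884/0.6116) = 2.43, a loss of 3%. At f = 4.3%, they become 0.5981 and 0.3828, and the OR is 2.40, a loss of 4%.
- OR 4.3, so p1 = 0.741. At f = 2.9% the OR is 4.05, a loss of 6%. At f = 4.3% it is 3.94, a loss of 8%.

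**Effect if they were dropped.** About 4% of births leave the first-trimester analyses.

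**The case against.** The strongest defence is that the Objectives also confine exposure to 1968–1985, so model and objective agree, and that eligibility may mean pregnancies lying wholly within those years. The second part does not fit the survey rule of residence at any time during pregnancy, or the birth-record reason for 1968. Even if it is granted, term births from 7 October to 30 December 1968 (85 of 6,575 days, 1.3%) still have a one-year window that opens in 1967.

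Other objections do stand, and they limit the point:

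- **Coding as unexposed.** A reader might infer that the plan will count these children as unexposed. No section says so. A child whose exposure is unknown does not meet the description of the reference group, and handling of missing exposure could be set out in an analysis plan.
- **Reach of the gap.** A reader might infer that 1968 births have no usable exposure. The one-year window lies wholly in 1967 only at the very start of 1968. For later births it lies only partly there. Mothers who moved on base in 1968 need no estimate of base water for 1967.
- **TCE.** Because "Before 1972, the Holcomb area was served by the Hadnot Point water distribution system", a reader might infer that the gap removes much of the TCE contrast. The protocol does not support this. The only contamination before 1968 that it calls likely is at Tarawa Terrace, where PCE was the main contaminant. Its Hadnot Point TCE measurements date from 1982–1985, and it describes the TCE situation as less clear.
- **Feasibility.** The protocol notes that historical contaminant data are scarce and that well-use logs were unavailable to earlier work. Nothing shows that usable 1967 operating data exist.

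**Conclusion.** The mismatch is real and follows from the protocol's own dates: a stated design parameter is set up to one year short of the exposure window that the study tests. It is minor and should be fixed, but it does not threaten the study. At most about 2.9% of births lose the whole first trimester, 4.3% lose at least part of it, and 5.6% lose part of the one-year window. That is roughly one case per outcome.

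Under the worst handling considered, which the protocol does not prescribe, odds ratios of 2.5 to 4.3 would be attenuated by roughly 3–8%. With so few cases, that is small beside the wide confidence intervals the Discussion already expects. These sizes rest on even births, term gestation, 40% exposure and loss unrelated to case status. The shares are upper bounds because some mothers were not on base in 1967.

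**What to change.** In the Exposure Assessment section, start the historical reconstruction and the monthly assignment (step II) in January 1967. The model would then match the one-year residential history that the questionnaire already collects.

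State a fallback as well. If 1967 operating data prove unusable, restrict each window-specific analysis to births whose on-base window is fully modelled, and do not code unmodelled on-base months as unexposed. A mother who came to the base only in 1968 stays in.

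The first option costs twelve more model months resting on sparse data, with no extra participants. The fallback costs up to about 4% of births in the first-trimester analyses, or 5.6% where the full one-year window is required.

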The informed consent for the 1999-2002 ATSDR survey (IRB No. 2544) included a clause that ATSDR or their representative may contact the participants to ask them to take part in future studies (Appendix III). Potential participants will be informed about the study by an initial contact letter describing the purpose and design of the study (Appendix IV). Two weeks after the letters are mailed out; contractors will call the potential participants and invite them to take part in the study by participating in a 45 minute long telephone interview. If the initial study participant is not the child's father, we will also attempt to contact the child's father so we can get more detailed information about the father's medical history, lifestyle habits, and occupational history.

Data Collection

Trained interviewers will administer a telephone questionnaire using a computer-assisted telephone interview (CATI) instrument. The questionnaire will be administered to the biological mother of the case or control child; questions that ask about the biological father's lifestyle habits and medical and occupational history during the time period of interest will also be administered to the biological father if available to obtain more detailed information. A verbal informed consent will be obtained before the first question is read (Appendix V). The questionnaire will collect information on demographic and personal characteristics such as mother's residential history for a one year period before and after the birth of the index child; maternal drinking water and other home water usage; mother's pregnancy history of the index child (fever, prenatal care, medications, etc.); parental history of birth defects or having a previous child with a birth defect; maternal smoking, alcohol use, and occupation; and father's lifestyle habits and occupational history (Appendix V). Select variables collected in the 1998 study and the subsequent 1999-2002 survey (i.e., maternal residential history, child's date of birth, and highest level of education) will be pre-loaded into the CATI instrument and verified with the respondent. The collected information will be used to assign exposure status and to assess potential confounding.

A training manual describing interviewing techniques, intent and instructions for each question, and

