All electronically entered information obtained from questionnaires will be reviewed for missing data and ambiguous responses. Individual interviewers will be contacted to complete missing data where possible or to call back participants to fill in the missing information. Internal consistency and validity programs will be used to identify and correct coding and data entry errors. Data entry will be verified for accuracy by using software data match features.

Reimbursement

No remuneration will be offered to participants. In addition, no invasive procedures will be performed which could potentially cause injury or the need for medical treatment.

Data Analysis

The exposure variables include exposure status, concentration level, and/or percent of water from a contaminated source during specific time periods of interest in the one-year period before the child's birth. TCE and PCE will be evaluated separately. The exposure metrics will be ever/never, a categorization of the contaminant levels, and a categorical exposure variable that incorporates water usage and consumption as well as contaminant levels. Categorical exposure variables will be used because of the uncertainties involved in estimating exposures. We will look at the distribution of contaminant levels to determine appropriate cutoff values for the categorical variables. Those exposed to TCE or PCE will be compared to those without exposure to either chemical in the drinking water. Extensive sensitivity analyses will be conducted on the water modeling.

Descriptive statistics will be presented for the potential risk factors. Verified cases of birth defects and childhood cancers will be compared with controls using unconditional logistic regression. It may be necessary to use exact or conditional logistic regression methods if the data are too sparse. We will consider doing a secondary analysis including unconfirmed cases because the true odds ratio lies between the results obtained by analyzing only confirmed cases and confirmed and unconfirmed cases because unconfirmed cases are not all negative (do not have the condition) or all positive (do have the condition).

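### The exposure metric as described is residential, so a mother with clean home water who worked on the TCE-contaminated Hadnot Point system would fall into the unexposed reference group

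*Protocol*

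**What the plan says.** The Objectives concern the mother's exposure to TCE and PCE in drinking water at Camp Lejeune in the year before birth; they are not restricted to water at home. The exposure elements described are these:

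- Exposure Assessment: "The exposure assessment methods in the current study will most likely estimate concentrations by year and housing complex". The one refinement foreseen is finer location inside a housing complex.
- Data Collection: the water-use items listed are "maternal drinking water and other home water usage". Maternal occupation is collected, and interview information in general is to serve exposure assignment and confounder assessment.
- Discussion: maternal address comes from housing records.
- Data Analysis: the metrics are ever/never, categories of contaminant level, and a category combining level with water use. The contrast is fixed as "Those exposed to TCE or PCE will be compared to those without exposure to either chemical in the drinking water".

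On the Hadnot Point system, the Introduction says: "This water distribution system supplied water primarily for industrial purposes at the base but it also supplied drinking water to the Hospital Point housing area". On the contamination found there, it reports: "High levels of TCE (a maximum of 1,400 ppb) were detected during sampling in 1982". The Holcomb area was on Hadnot Point water before 1972 and again for 12 days in early 1985.

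**The concern.** A residential metric cannot by itself guarantee that the reference group had no contact with either chemical. This site makes the gap relevant. After 1972, and apart from the 12-day hookup, Hospital Point is the only housing area the protocol names on the TCE system, so most of that system lay outside housing. A mother with clean home water and a job in the Hadnot Point area would be counted as unexposed. A mother in Tarawa Terrace with such a job would be counted for PCE, but her workplace TCE would not be credited.

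The same reference group serves the TCE and the PCE comparison, so an error there reaches both. TCE is the more fragile of the two, because the sample-size section already expects a large majority of births to be unexposed to it. A weak TCE result could then be read as no association. The Discussion calls the exposures well defined and deals with address and recall error, but does not mention water drunk away from home. The planned sensitivity analyses are on the water model: they vary the concentrations, not where the mother drank.

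**Working it through.** **The plan's own figures.** The detectable odds ratios (Sample Size, Power, and Precision of Risk Estimates) reproduce with the two-proportion formula with continuity correction, two-sided alpha 0.10 and 40% of controls exposed. For 28 NTD cases, 448 controls and OR 2.85, case exposure is 2.85 × 0.40 / (0.60 + 2.85 × 0.40) = 0.655, and the formula asks for 28 cases. All six statements agree within two cases. They are not in dispute.

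**Inputs for the check.** From the protocol: 25 NTD cases and 710 controls (the 90% participation yield), alpha 0.10. Assumed, because the protocol gives no figure: true OR 3; 10% of controls TCE-exposed at home; f, the share of home-unexposed controls with Hadnot Point water at work; and a workplace odds ratio OR_w of either 3 (equal effect) or √3 = 1.732 (weaker effect).

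**Attenuation.** Observed OR = OR / ((1 − f) + f × OR_w). At f = 10%, equal effect: 3 / (0.9 + 0.3) = 2.50. At f = 10%, square-root effect: 3 / (0.9 + 0.173) = 2.80.

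| f | Equal effect | Square-root effect |
|---|---|---|
| 2% | 2.88 | 2.96 |
| 5% | 2.73 | 2.89 |
| 10% | 2.50 | 2.80 |
| 20% | 2.14 | 2.62 |

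**Power at f = 10%.** Two-proportion normal approximation without continuity correction: power = Φ[(difference − 1.645 × SE0) / SE1], with SE0 pooled and SE1 unpooled. Control shares are 0.10 home-exposed, 0.9 × 0.1 = 0.09 workplace only, and 0.81 unexposed.

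- Equal effect, home-only classification: case weights are 0.30, 0.27 and 0.81, total 1.38. Case exposure is 0.30 / 1.38 = 0.217 against 0.10. Power is about 57%.
- Equal effect, workplace-only mothers set aside: 20.1 cases and 646 controls remain. Exposure is 0.30 / 1.11 = 0.270 against 0.10 / 0.91 = 0.110. Power is about 66%.
- Square-root effect, home-only: weights are 0.30, 0.156 and 0.81, total 1.266. Case exposure is 0.237. Power is about 66%.
- Square-root effect, set aside: 21.9 cases remain, with the same 0.270 against 0.110. Power is about 69%.
- Pooling the workplace-only mothers with the home-exposed instead gives about 82% (equal effect) or 65% (square-root effect).

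The example treats all births not TCE-exposed at home as the reference. In the planned contrast, births exposed only to PCE at home would leave it, so absolute power would be lower. The continuity correction also lowers the levels (for the 28-case NTD statement, from 85% to 80%). The comparison between rows is what matters here.

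**The case against.** Several points against pressing this further have weight.

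- **The text is less absolute than it looks.** A reader might infer that exposure is fixed at the home tap alone. The housing-complex sentence is hedged. The modelling technique "can provide the proportional contribution of water from a water source to any location serviced by the water-distribution system", and the plan foresees "assignment of the monthly contaminant concentrations for historical period for all study locations". Occupation is collected, and Appendix V is not available here. This shows that workplace water could be included; it does not show that it will be, since no metric listed under Data Analysis uses it.
- **The share of mothers concerned is undocumented.** A reader might take it as established that the reference group contains exposed mothers, pointing to "A referral process was used to obtain information on personnel who were pregnant while residing at Camp Lejeune during 1968-1985 but who delivered elsewhere". That section uses the word personnel loosely, and nothing says how many mothers worked, on base or on Hadnot Point water. If f is near zero the issue disappears.
- **Equal effect is probably too strong.** The toxicology section expects more exposure from inhalation than from ingestion, and most of the activities it lists (bathing, showering, cooking, washing machines, dishwashers) are mainly done at home. The square-root column may be nearer the mark.
- **Recall.** The plan uses housing records precisely to avoid address recall. Workplace location would rest on memory over 28-35 years, sometimes that of a father or child. If recall differs between cases and controls, the direction of bias becomes unknown.

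The last point stands in full, and it decides that the workplace analysis should not replace the residential one.

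**Conclusion.** The point holds in a limited form. The metric as described is residential while the TCE system served mainly non-residential uses, so workplace exposure among mothers with clean home water would enter the reference group. Under non-differential error, that contamination lowers the ever/never TCE odds ratio, and the PCE odds ratio too where workplace TCE itself raises risk. Attenuation is not assured for every level of a multi-category metric.

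The size depends on f. A true odds ratio of 3 stays at 2.88 or above at f = 2%, and falls to between 2.50 and 2.80 at f = 10%.

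Two stronger conclusions are not supported. First, no exposed births are discarded: they move into the reference group, and only where the home supply was clean. Holcomb-area residents before 1972 already count as TCE-exposed. Second, a power gain from 57% to 82% needs both pooling and an equal workplace effect. Setting the mothers aside gives 57% to 66%, or 66% to 69% under the weaker effect, where pooling gains nothing. The case for the change is chiefly a cleaner reference group.

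**What to change.** - Unless Appendix V already does so, have the maternal occupation section record, for each job in the year before birth, whether it was on base, in which area, and the dates. Map that area to one of the three water systems and its modelled concentrations.
- Keep the record-based residential metric as primary.
- Prespecify a sensitivity analysis that removes mothers with on-base work in a contaminated-system area from the reference group, or shows them as a separate category.
- State in Data Analysis whether workplace water enters any metric, and name non-residential water as a limitation in the Discussion.

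The cost is at most a few interview items in a section already planned, and a look-up from base area to water system. It should be done before interviewing starts, since the information is hard to recover later. The drawback is long and sometimes proxy recall of workplace, which is acceptable in a sensitivity analysis.
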